### **8.3. Clinical Laboratory Analyses**

Laboratory evaluations including the analyses of Chemistry laboratory tests, Hematology laboratory tests and liver function tests will be based on GSK Core Data Standards.

### **8.4. Spirometry**

The estimand is the effect of actual treatment in the population of participants who were randomised and dosed.

A frequentist MMRM analysis will be performed on spirometry data.

#### **8.4.1. Endpoint**

Change from baseline in post-BD FEV1

Change from baseline in post-BD FVC

#### **8.4.2. Summary Measure**

The summary measure is the adjusted mean difference from placebo for each danirixin dose.

#### **8.4.3. Population of Interest**

mITT population.

#### 8.4.4. Strategy for Intercurrent (Post-Randomization) Events

The intercurrent event of interest is treatment discontinuation. A ‘hypothetical’ strategy will be used to account for this event. All recorded data up to the time of treatment discontinuation will be included in the analysis. Subsequent data up to Day 168 will be assumed to be missing at random (MAR).

#### 8.4.5. Statistical Analyses / Methods

##### 8.4.5.1. Frequentist MMRM Methodology Specification

Endpoint / Variables

 
Change from baseline in post-BD FEV1
 
Change from baseline in post-BD FVC
 

Model Specification

 
The following covariates will be included in the model: baseline, country, smoking status at screening, treatment, Visit, Visit *baseline and Visit *treatment interactions, where Visit is nominal. Visit will consist of two levels (Day 84 and 168), and treatment will consist of six levels (placebo and 5 active doses)
 
Two models will be fitted; one with a response variable (FEV1 or FVC), and one with a response variable of change from baseline (FEV1 or FVC).
 
An unstructured covariance structure for the R matrix will be used by specifying ‘type=UN’ on the REPEATED line.
 
The Kenward and Roger method for approximating the denominator degrees of freedom and correcting for bias in the estimated variance-covariance of the fixed effects will be used. If this method does not run, the residual method will be used instead
 
The OM option will be used to derive the least square (LS) means using coefficients which are based on the participants used in the analysis. The OM option requires an OM dataset which has a row for every participant-visit combination that contains all of the covariates used in the model and a macro variable containing the mean baseline for the participants used in the analysis.
 

Model Checking & Diagnostics

 
Distributional assumptions underlying the model used for analyses using MMRM will be examined by obtaining a normal probability plot of the residuals and a plot of the residuals versus the fitted values (i.e. checking the normality assumption and constant variance assumption of the model respectively) to gain confidence that the model assumptions are reasonable. Plots of residuals versus covariates and baseline versus response will also be examined.
 

Model Results Presentation

 
LS mean and LS mean changes from baseline with their corresponding standard errors (SEs) for each visit and each treatment
 
Estimated treatment differences from placebo and corresponding 90% confidence intervals (CIs) and p-values for each visit and each danirixin dose.
 
A figure of LS mean changes from baseline and 90% CIs for each treatment by visit will be generated.
 
The type III tests of fixed effects from the model will be presented.
 

### Summary Results Presentation

- Summary statistics for baseline post-BD FEV1, FVC and FEV1/FVC for each treatment and overall for participants with non-missing assessments for each Visit, for the mITT population.
- Summary statistics for raw and change from baseline post-BD FEV1, FVC and FEV1/FVC for each visit for each treatment, for the mITT population.
- A figure of mean and 90% CIs for each treatment by visit (including baseline, Day 84 and Day 168) will be generated for post-BD FEV1, FVC and FEV1/FVC.

## 8.5. Other Safety Analyses

The analyses of non-laboratory safety test results including ECGs and vital signs will be based on GSK Core Data Standards, unless otherwise specified.

## 9. PHARMACOKINETIC ANALYSES

### 9.1. Primary Pharmacokinetic Analyses

#### 9.1.1. Derived Pharmacokinetic Parameters

PK parameters will be calculated by standard non-compartmental analysis according to current working practices and using the currently supported version of WinNonlin. All calculations of non-compartmental parameters will be based on actual sampling times. PK parameters listed will be determined from the blood concentration-time (dry blood spot) data at Visit 3 and 10, as data permits for participants in the PK sub-set collecting PK samples at pre-dose, 0.5, 1, 2, 4, 6, 8, 10, 12 hours post-dose.

Parameter	Parameter Description
AUC(0-t)	Area under the concentration-time curve from time zero to the time of the last quantifiable concentration (C(t)) will be calculated using the linear trapezoidal rule for each incremental trapezoid and the log trapezoidal rule for each decremental trapezoid.
Cmax	Maximum observed concentration, determined directly from the concentration-time data.
Tmax	Time to reach Cmax, determined directly from the concentration-time data.
Tlast	Time of last quantifiable concentration

#### NOTES:

- Additional parameters may be included as required.

#### 9.1.2. Statistical Analyses / Methods

No formal statistical analysis of the dry blood spot PK concentrations or PK parameters will be performed. Details of the planned displays are provided in [Appendix 11](#) and will be based on GSK Data Standards and statistical principles.

## 9.2. Exploratory Pharmacokinetic Analyses

### 9.2.1. Derived Pharmacokinetic Parameters

Note: Approximately 20% of the wet whole blood samples collected at Visit 3 will be analysed for danirixin concentrations to provide an analytical comparison between dried blood spot and wet whole blood sample results. The expectation is that samples selected will mainly come from those samples provided by participants in the PK sub-set (i.e. collecting samples over 12 hours) and be distributed across danirixin treatment groups.

PK parameters will be calculated by standard non-compartmental analysis according to current working practices and using the currently supported version of WinNonlin. All calculations of non-compartmental parameters will be based on actual sampling times. PK parameters listed will be determined from the blood concentration-time (wet whole blood) data at Visit 3, as data permits.

Parameter	Parameter Description
AUC(0-t)	Area under the concentration-time curve from time zero to the time of the last quantifiable concentration (C(t)) will be calculated using the linear trapezoidal rule for each incremental trapezoid and the log trapezoidal rule for each decremental trapezoid.
Cmax	Maximum observed concentration, determined directly from the concentration-time data.
Tmax	Time to reach Cmax, determined directly from the concentration-time data.
Tlast	Time of last quantifiable concentration

#### NOTES:

- Additional parameters may be included as required.

### 9.2.2. Statistical Analyses / Methods

Details of the planned displays are provided in [Appendix 11](#) and will be based on GSK Data Standards and statistical principles.

Unless otherwise specified, endpoints / variables defined in Section 9.2.1 will be summarised using descriptive statistics, graphically presented (where appropriate) and listed.

#### 9.2.2.1. Statistical Methodology Specification

An extension of the Bland and Altman approach [[Bland, 1986](#); [Bland, 1999](#)] will be used to quantify the agreement between the assay methods using log-transformed data, including hematocrit in the model. Age and weight will also be added one at a time in a model building approach and their significance in the model will be assessed. Limits of agreement and the coefficient of variation will be assessed to determine the agreement of the assay methods and whether wet whole blood assay is comparable to dry blood spot assay.

A sensitivity analysis will be performed excluding dry blood spot concentrations above the assay higher level of quantification of 1000 ng/mL.

Endpoint / Variables

 
Log-transformed Danirixin blood concentration and pharmacokinetic parameter (Cmax and AUC(0-t)) data
 

Model Specification

 
The Bland and Altman method will be used.
 
The following covariates will be included in the model: haematocrit, age and weight.
 

Model Results Presentation

 
Separate outputs will be produced for Danirixin concentration and pharmacokinetic parameters (although both will be analyzed using the same model)
 
Estimates of intercept and slope on log-scale for Danirixin concentration and pharmacokinetic parameters, bias at concentration is 0, %CVw, geometric means and limit of agreement at concentration is 0.
 
Comparative plots of individual blood concentration and pharmacokinetic parameter data.
 
Supportive SAS output from statistical analysis.
 

Sensitivity and Supportive Analyses

 
A sensitivity analysis excluding dry blood spot concentrations above the assay HLOQ of 1000 ng/mL will be performed.
 

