9.5. Pharmacokinetics

- Whole blood samples of approximately 2 mL will be collected for measurement of whole blood concentrations of danirixin (performed under the control of GSK Platform Technology and Science Department of In Vitro In Vivo Translation Third Party Resourcing (PTS-IVIVT/TPR)) as specified in the SoA ([Table 1](#)). Instructions for the collection, processing, storage and shipping of biological samples will be provided by the sponsor in the SRM. The actual date and time (24-hour clock time) of each sample will be recorded.
- Samples will be used to evaluate the PK of danirixin at Visit 3 and 10. Each whole blood sample will be used to prepare 4 dried blood spots which will be analysed for danirixin concentrations and reported as primary data. The remaining whole blood will be retained and approximately 20% of the wet whole blood samples collected in Visit 3 will also be analysed for danirixin concentrations to provide an analytical comparison between dried blood spots and wet whole blood sample results. Samples collected for analyses of danirixin whole blood may also be used to evaluate safety or efficacy aspects related to concerns arising during or after the study.

- Any remaining whole blood will be stored and may be analyzed for other compound-related metabolites and the results reported under a separate protocol.

Drug concentration information that may unblind the study will not be reported to investigative sites or blinded personnel until the study has been unblinded.

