#### **14.9.1.5. Dataset Specification**

General description and rules:

- Missing or unknown values in covariates, if not to be imputed, will be assigned -99.
- The dataset is sorted by STUD, SUBJID, DATE, RTFD, EVID descending.
- The data items (columns) in the analysis-ready data file will be provided in the same order as follows.
- NQ concentration values will be included as detailed for the CONC variable.
- Non-numerical concentration values (such as NS, NR, NA) will not be included.
- Placebo participants will not be included.
- The dataset will be a comma delimited ASCII text file and will be named:
  - *NM.compound.study.PK.v1.csv*
  - Where “compound” is the compound name (e.g. GSK1234567) and “study” is the study number (e.g. 205724).

Variable	Label (Variable description)	Type	Units	Missing value	Codes/Derivation/Notes
ID	NONMEM participant identifier	Integer	None	Never	Sequential participant identifier across study after data is sorted by STUD, SUBJID, DATE, RTFD, EVID. Numbering to start at 1. To be entered in all rows for each participant.
STUDYID	Unique identifier for a study	Char	None	Never	205724 for all records
STUD	Study ID	Num	None	Never	205724 for all records
SUBJID	Participant identifier for study	Num	None	Never	Participant identifier, which must be unique within the study. The identification number of the participant as recorded on the CRF. Exclude placebo participants. Include participants who have received IP and have at least one measurable drug concentration. To be entered in all rows for each participant.
COUNTRY	Country	Char	None	Never	Country of the investigational site in which the participant participated in the trial; e.g. USA. To be entered in all rows for each participant.
SITEID	Unique identifier for a study site	Char	None	Never	e.g. PPD any lead zero should not be included. To be entered in all rows for each participant.
CONC	Drug Concentration	Num	ng/mL	Never	CONC=0 for DOSE_GSK1325756 records. No sample (NS), insufficient sample (IS) and no result (NR) records will be excluded from dataset. CONC='.' for PK_GSK1325756 records < LOQ (i.e. if drug conc is NQ).
LNCONC	Natural log of CONC column	Num	ng/mL	Never	Natural log of CONC column. If CONC=0, then LNCONC='.'
LLQ	Lower Limit of quantification	Num	ng/mL	Never	LLQ=5 or from source data if different. To be entered in all rows for each participant.

Variable	Label (Variable description)	Type	Units	Missing value	Codes/Derivation/Notes

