## 14.11.11. Pharmacokinetic / Pharmacodynamic Figure

Pharmacokinetic / Pharmacodynamic: Figures					
SAC No.	Population	IDSL / Example Shell	Title	Programming Notes	Deliverable [Priority]
5.1	PK		Scatter plot of PD endpoint versus Danirixin Concentration (Trough)	CAT Total Score Include Placebo imputed as DNX conc=0ng/mL, include DNX conc=NQ imputed as LLOQ/2, where LLOQ=5ng/mL By Day Different symbol for each treatment	Post SAC
5.2	PK		Scatter plot of Safety versus Danirixin Concentration (Trough)	Blood Neutrophil Count and C-reactive Protein (CRP) Highlight subjects with an on-treatment event in the 'Infective pneumonia' SMQ. Add footnote 'Note: Pneumonia may have occurred at any time during the study' Include Placebo imputed as DNX conc=0ng/mL, include DNX conc=NQ imputed as LLOQ/2, where LLOQ=5ng/mL By Day Different symbol for each treatment	Post SAC
5.3	PK		Quartile plot of Danirixin Concentration versus PD endpoint	CAT Total Score	Post SAC
5.4	PK		Quartile plot of Danirixin Concentration versus Safety endpoint	Blood Neutrophil Count and C-reactive Protein (CRP)	Post SAC

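### The tabulated bias and limits of agreement between dried blood spot and wet whole blood are taken at a zero point that, unless log concentration is centred, lies outside the assay range

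*SAP*

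**What the plan says.** Protocol 9.5 has each whole blood sample used to prepare "4 dried blood spots which will be analysed for danirixin concentrations and reported as primary data", and about 20% of the Visit 3 wet whole blood samples assayed as well for comparison. SAP 9.2.2.1 plans to "quantify the agreement between the assay methods using log-transformed data, including hematocrit in the model", with age and weight as further candidate covariates. The endpoints are concentration, Cmax and AUC(0-t).

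The listed results begin with "Estimates of intercept and slope on log-scale for Danirixin concentration and pharmacokinetic parameters" and continue with "bias at concentration is 0, %CVw, geometric means and limit of agreement at concentration is 0". Comparative plots follow. The use of these results is stated: "Limits of agreement and the coefficient of variation will be assessed to determine the agreement of the assay methods". No acceptance limit is set.

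The SAP gives no model equation. It does not say whether log concentration is centred, or at what haematocrit, age or weight the zero-point results are evaluated. Elsewhere it puts the quantification limit at 5 ng/mL: "LLQ=5 or from source data if different" in the population PK dataset specification (14.9.1.5) and "where LLOQ=5ng/mL" in the PK/PD figure notes (14.11.11). The dried blood spot upper limit in 9.2.2.1 is 1000 ng/mL.

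**The concern.** A concentration of zero has no logarithm. The SAP's own population PK rules recognise this by setting the log of a zero concentration to missing. If the phrase means log concentration equal to zero, the point is 1 ng/mL, where no quantifiable sample can lie.

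Bias and limits of agreement at that point equal those at study concentrations only if the difference between assays does not change with concentration. The plan estimates a slope, so it does not take that for granted. At stake is the numeric summary on which comparability of the two assays is to be judged: two methods that agree well over the observed range could be tabulated as biased, or the reverse.

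**Working it through.** The plan states no figure to reproduce, so the check is on the reporting point itself.

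**Inputs from the documents.** Quantification limit 5 ng/mL (SAP 14.9.1.5 and 14.11.11); dried blood spot upper limit 1000 ng/mL (SAP 9.2.2.1); predicted steady-state values from Protocol Table 2: 5 mg Cmin 5th percentile 6.8 ng/mL, and median Cavg 57.2 ng/mL at 5 mg and 571 ng/mL at 50 mg. The compared samples come from Visit 3, which is Day 1, so the Table 2 values are only a guide to scale.

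**Assumed model.** d = a + b ln(C), where d is the log ratio of the two assays and C the concentration, uncentred. The documents give no slope; values from -0.1 to 0.1 were tried.

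**Where the zero point lies.** ln(C) = 0 gives C = exp(0) = 1 ng/mL. This is also 1 ng/mL with base-10 logs. Against the quantification limit, 1/5 = 0.2. It is also below 6.8 ng/mL and far below 57.2 to 571 ng/mL.

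**Size of the extrapolation.** Tabulated bias = exp(a). Bias at C = exp(a + b ln C) = exp(a) × C^b. With a residual SD that does not depend on C, the limits exp(a + b ln C ± 1.96 SD) move by the same factor. The factor C^b is:

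| C (ng/mL) | b = -0.05 | b = -0.02 | b = 0 | b = 0.02 | b = 0.05 |
|---|---|---|---|---|---|
| 5 | 0.92 | 0.97 | 1.00 | 1.03 | 1.08 |
| 57.2 | 0.82 | 0.92 | 1.00 | 1.08 | 1.22 |
| 571 | 0.73 | 0.88 | 1.00 | 1.14 | 1.37 |
| 1000 | 0.71 | 0.87 | 1.00 | 1.15 | 1.41 |

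For example, ln(571) = 6.35, and exp(0.05 × 6.35) = 1.37. At b = ±0.1 the factor at 1000 ng/mL is 2.00 or 0.50.

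**AUC(0-t).** Log zero means 1 ng.h/mL or 1 µg.h/mL, depending on the unit used. The two points differ by a factor of 1000, so the tabulated bias changes by 1000^b: 1.41 for b = 0.05, 0.71 for b = -0.05.

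**Illustration by simulation.** All settings are assumed: 400 pairs; log concentrations drawn around ln(120) with SD 1.2 and truncated to 5 to 1000 ng/mL; residual SD 0.15; slope 0.05; true ratio 1.00 at 120 ng/mL.

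| Reporting point | Bias | Limits of agreement | SE of log bias |
|---|---|---|---|
| Mean log concentration | 1.00 | 0.74 to 1.34 | 0.0075 |
| ln(C) = 0 | 0.79 | 0.59 to 1.06 | 0.032 |

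The same data therefore give a bias about 21% lower, with about four times the standard error, purely from the choice of reporting point. With slope 0 both points give a bias of 1.00, and only the precision differs.

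**The case against.** A reader might infer that the plan leaves agreement at study concentrations undescribed. It does not. Intercept, slope and %CVw are reported, so bias at any concentration can be worked out and the limits approximated. Appendix 11 plans individual, comparative and Bland-Altman plots of concentrations over the observed range (Figures 4.8 to 4.10), with versions that exclude values above 1000 ng/mL (Figures 4.11 to 4.13). Tables 4.5 and 4.8 add a further comparison of the PK parameters. This stands, and it limits the point to the tabulated bias and limits. It does not remove it, because those limits are the named basis for the judgement. Figures 4.8 to 4.13 also cover concentrations only; Appendix 11 lists no dried-versus-wet plot of Cmax or AUC, although SAP 9.2.2.1 calls for comparative plots of the parameters.

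A second objection is that the model is inferred. Concentration is not in the SAP's covariate list, and the regressor may be mean-centred, in which case zero is the sample mean and the problem disappears. That is possible. The SAP does not say so, and stating it is part of the fix.

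A reader might also infer that the primary PK results or the exposure margin for testicular effects depend on this number. The documents do not support that. The comparison is exploratory, has no acceptance limit and carries no stated consequence. The primary PK analysis uses dried blood spots regardless (SAP 9.1.1), and the margin in Protocol 5.5 concerns predicted AUC(0-24), not Day 1 Cmax or AUC(0-t).

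**Conclusion.** The point holds for the tabulated bias and limits of agreement only. Unless log concentration is centred, they refer to an undefined point or to 1 ng/mL, below the quantification limit, and for AUC(0-t) to a point set by the choice of unit. They are then an extrapolation whenever the slope is not zero. Under the assumed slopes of -0.05 to 0.05, the factor at 571 ng/mL runs from 0.73 to 1.37 and is exactly 1.00 at slope zero.

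This rests on three assumptions: a linear dependence on uncentred log concentration, slopes that no document supplies, and steady-state predictions standing in for Day 1 concentrations. The 5 ng/mL limit is taken from other parts of the SAP. The primary efficacy analysis is not affected. It is a modest correction to an exploratory summary, worth making because the plan names that summary as a basis for its conclusion.

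**What to change.** In SAP 9.2.2.1, write out the model, including the regressor, and state whether log concentration and the covariates are centred. Replace the two results at zero concentration with back-transformed bias and limits of agreement:

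- for concentrations, at the mean log concentration and at a few stated values within the observed Visit 3 range, between 5 and 1000 ng/mL;
- for Cmax and AUC(0-t), at the geometric mean of each dose group, with units stated;
- in every case at mean haematocrit and at the mean of any other covariate kept in the model.

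Intercept and slope can stay as supporting output. The cost is SAP wording, an estimate statement and a matching change to the affected table shells. No new samples or data are needed.

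If the regressor is already mean-centred, one sentence saying so, with the covariate values used, removes the extrapolation problem for concentrations.

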## 10. POPULATION PHARMACOKINETIC ANALYSES

PK data from this study may be combined with historic data for the purposes of population PK (PopPK) modelling which would be the subject of a separate analysis plan and would be presented separately from the main CSR.

To support this analysis a PopPK dataset will be generated. The details for the dataset specifications are provided in [Appendix 9](#).

## 11. BIOMARKER ANALYSES

C-reactive protein and fibrinogen data will be summarized in the same way as laboratory data. Summary tables and boxplots for each treatment by visit (including screening, baseline, Day 84 and Day 168) will be generated for the mITT populations and also for the subset of subjects who have an event in the 'Infective pneumonia' SMQ.

Exploratory biomarker analysis will be the subject of a separate RAP.

## **12. PHARMACOKINETIC / PHARMACODYNAMIC ANALYSES**

Graphical assessment of the relationship between individual danirixin exposure and PD endpoints will be conducted.

Contingent on any PK/PD relationship(s) being identified from the graphical assessment a PK/PD dataset will be generated. The details for the methodology and dataset specifications will be provided in a separate document after review of the graphical assessment of the relationship between PK and PD endpoints.

### **12.1. Statistical Analyses / Methods**

Details of the planned displays are provided in [Appendix 11](#) and will be based on GSK Data Standards and statistical principles.

## 14. APPENDICES

### 14.1. Appendix 1: Protocol Deviation Management and Definitions for Per Protocol Population

#### 14.1.1. Exclusions from Per Protocol Population

A participant meeting any of the following criteria will be excluded from the Per Protocol population:

Number	Exclusion Description
01	Inclusion #2 – FEV1/FVC ratio $\geq 0.70$ or % predicted FEV1 $< 40\%$ at Screening
02	Inclusion #4 – $< 2$ historical exacerbations or one historical exacerbation with screening fibrinogen $< 3$ g/L
03	Inclusion #5 - Smoking history of $< 10$ pack years at Screening
04	Exclusion #4 - Screening visit is less than 14 days since the completion of a course of antibiotics or oral steroids for a COPD exacerbation
05	Exclusion #14 - Use of PDE4 inhibitors within 30 days of Screening
06	Exclusion #26 - Oxygen use that is not PRN at Screening

At the strategic interim a participant meeting any of the following criteria will be excluded from the Per Protocol population:

Number	Exclusion Description
07	Xanthines at any time between the day after screening and end of treatment
08	PDE4 inhibitors at any time between screening and end of treatment
09	Chronic use (more than 3 months) of erythromycin or azithromycin for between screening and end of treatment
10	Participants who stopped study medication for more than 14 days
11	Blind broken

For the final analysis a participant meeting any of the following criteria will have data excluded from the time of the deviation. If a prohibited medication is taken prior to randomisation the participant will be excluded from the Per Protocol population.

Number	Exclusion Description
07	Xanthines at any time between the day after screening and end of treatment
08	PDE4 inhibitors at any time between screening and end of treatment
09	Chronic use (more than 3 months) of erythromycin or azithromycin between screening and end of treatment
10	Participants who stopped study medication for more than 14 days will be excluded from the PP analyses from the time they stopped taking study medication.
11	Data excluded from date of breaking of blind.

